3.3. HAWAII—PACIFIC HEALTH RESEARCH INSTITUTE

The Hawaii center is located in Honolulu, Hawaii at the Pacific Health Research Institute. Partners in this project with the Pacific Health Research Institute (PHRI) at the Hawaii Center will include Kaiser Permanente-Hawaii, the Hawaii Medical Service Association (HMSA), and the State of Hawaii Department of Human Services, Med-QUEST Division. For the prevalence component of the study, children with diabetes who are members the major health plans in Hawaii (the Hawaii Medical Service Association (HMSA), Kaiser Permanente-Hawaii and the State of Hawaii, and Department of Human Services Med-QUEST) in 2001 and reside on Oahu will be asked to participate. For the

incidence component of the study, case ascertainment will be expanded to include members of these three health plans on all the six major islands of Hawaii (Oahu, Hawaii, Maui, Kauai, Molokai and Lanai). The combined membership of these three plans includes over 90% of the state's non-military residential population under age 20 as determined by the US Census.

The Pacific Health Research Institute (PHRI) is a non-profit research institute created in 1960. Since 1996, HMSA and Kaiser Permanente-Hawaii have been contributing data to the Hawaii Diabetes Data Network (HDDN). For the prevalence component of SEARCH, the Hawaii center will use the information in the existing computer database. For the incidence component of SEARCH, cases will be identified using a rapid reporting system of clinics and physicians.

The Hawaii center will use administrative membership databases from the participating health systems as the source of denominator information. Estimates of the number of children in each ethnic group will be made based on the U.S. census with the assumption that the membership of the health plans is representative of the geographic base from which cases are drawn.

In 2000, approximately 300,000 children and adolescents less than 20 years of age resided on the six Hawaiian islands, including approximately 70% Asian and Pacific Islanders. All patients in the state's Medicaid program. (Med-QUEST) will be included.

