For the geographically based centers (Cincinnati, Colorado, Seattle, South Carolina), Census data by age, gender and race/ethnicity will be used to estimate the number of persons in the denominator by age, gender and race/ethnicity. Year 2000 Census data will be used to calculate age, gender, and race/ethnicity specific denominators.

For the membership-based Hawaii center, it will be assumed that membership in the participating health plans is representative of the population of Hawaii with regard to race/ethnicity. The Census proportions of the Hawaii population aged 0-19 years by race/ethnicity will be applied to the age and sex-specific membership denominators.

For the membership-based Southern California center, direct counts of members 0-19 years by age and gender will be obtained from membership records. Data on race/ethnicity will be obtained by linking address information to block-level data from the Census using a process called geocoding.

For all centers, race/ethnicity data will be collapsed into groups (Non-Hispanic white, Hispanic American, African American, Asian, Pacific Islander, Native American, Other and Unknown) using rules and conventions developed by the Census.

Age, Gender, and Race/Ethnicity: Incidence

For years 2002 and beyond of the incidence study, the geographically-based sites (Cincinnati, Colorado, Seattle, South Carolina) will use projections of population changes that are based on the 2000 Census. The methods for making these projections will vary by location, but will be standardized as much as possible across sites using demographically acceptable methods. Population projections may not be available by age, gender, and race/ethnicity at the level of detail needed. Projected denominators, therefore, will be estimated using 2000 Census proportions by gender and race/ethnicity within age-specific groups, at least through 2005.

For the membership-based centers (Hawaii and Southern California), membership counts by age and gender will be updated annually. For each of these sites, Census projections of race/ethnicity will be applied to the updated member-based denominators.

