4.1. DENOMINATOR ESTIMATION

4.1.1. Site specific approaches

The denominator for the Hawaii SEARCH site is the combined, non-duplicated membership of three large health care plans, which collectively include approximately 90% of the state's population. These organizations specifically include:

Hawaii Medical Service Association (HMSA) – Hawaii's Blue Cross/Blue Shield carrier, membership of approximately 640,000 individuals. SEARCH Project Co-Investigator: [name].

Kaiser Permanente Hawaii – Approximately 210,000 members. Search Project Co-Investigator: [name].

Hawaii State Department of Human Services, Med-QUEST Division – Includes approximately 130,000 medicaid-eligible individuals, as well as other traditionally uninsured individuals. SEARCH Project Co-Investigator: [name].

Total unduplicated plan membership for ages 0-19 based on 1997 data was 300,786, with 48% in the 0-9 age group and 52% in the 10-19 age group. We assume approximately equal distribution for all race/ethnic groups.

Race/ethnicity data are not available from these health plans. To estimate the proportions of each category agreed upon for the SEARCH project (Caucasian, African-American, Hispanic, Asian, Pacific Islander, and Native American), we applied proportions based on the 2000 Census data for Hawaii. For the actual study time period, membership data from the health plans will either be geocoded to estimate race/ethnicity proportions and/or a survey of a random sample of members will be conducted to collect race/ethnicity information.

The use of health plan membership as the denominator for our site offers distinct advantages in terms of enhanced completeness of ascertainment. In addition, because these plans include a large percentage of the state's population, including state-wide geographic membership including urban and rural, private and publicly insured members, we anticipate that our findings will be generalizable to the state of Hawaii as a whole.

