4.1.2. Denominators for prevalence

For prevalence case ascertainment, the denominator includes individuals enrolled in any of the three partnering health care plans and residing on the island of Oahu during the year 2001 (Oahu residents comprise approximately 80% of the state’s population).

	Caucasian	African American	Hispanic	Asian	Pacific Islander	Native American	Total
0 thru 9	26295	3310	13733	50754	20914	319	115325
10-19	28486	3585	14877	54984	22657	346	124935
	54781	6895	28610	105738	43571	665	240260

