Cases that are between the ages of 0 and 19.999 during the selected index year (2001) will be eligible for inclusion in the study. Geographic eligibility for the Hawaii study center for prevalent cases will be limited to members of the HMSA, Kaiser Permanente and Med-QUEST health plans who reside on the island of Oahu (Honolulu County). The population of Honolulu County includes approximately 80% of the population of the entire state. All data sources to be used for initial case identification include zip codes in their membership files and Oahu residents can be readily identified on the basis of zip code.

a) Case Definition 1: HMSA Data

Designed primarily for billing purposes, this data source is typical of insurance claims datasets with considerable administrative information and little clinical information. Specific algorithms have been developed for identification of diabetic individuals using similar and sensitive data. However, the relative accuracy of these methods for identifying children with diabetes is unknown. Given the potential for misdiagnosis of hyperglycemic episodes in children we

anticipate less specificity of this method in the identification of children. Anecdotal evidence suggests a reluctance among Hawaii practitioners to utilize oral hypoglycemic agents in children however, which may result in fewer false positive cases based on this criteria in Hawaii than in other sites.

The specific criteria for initial case identification from this source include any one of the following:

- At least one prescription for insulin or oral anti-diabetic agent included in HEDIS list for the identification of persons with diabetes during the index year.
- A principal or secondary inpatient discharge ICD-9-CM diagnosis of diabetes (250.xx) during the index year. Diagnosis code 648.0x for gestational diabetes will be excluded.
- In outpatient claims, one visit with a diagnosis of diabetes (250.xx) during index year. Diagnosis code 648.0x for gestational diabetes will be excluded
- From laboratory claims or utilization files, at least two glycohemoglobin or fructosamine tests done on separate dates during the index year (CPT-4 codes 83036 or 82985).

b) Case Definition 2: Kaiser Permanente Hawaii Data

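### Hawaii prevalence is restricted to Oahu, but the common protocol takes race denominators from one statewide under-20 mix, and two other sections describe the method differently

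*Protocol*

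**What the plan says.** **Population.** The Hawaii site section 4.1.2 states that "the denominator includes individuals enrolled in any of the three partnering health care plans and residing on the island of Oahu during the year 2001". The case side matches: "Geographic eligibility for the Hawaii study center for prevalent cases will be limited to members of the HMSA, Kaiser Permanente and Med-QUEST health plans who" live on Oahu (Hawaii 4.2.1.1). Incidence is statewide (Hawaii 4.1.3).

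**Race, common protocol.** Section 4.2, in the prevalence part on age, gender and race/ethnicity, says that "it will be assumed that membership in the participating health plans is representative of the population of Hawaii with regard to race/ethnicity". It then gives the rule: "The Census proportions of the Hawaii population aged 0-19 years by race/ethnicity will be applied to the age and sex-specific membership denominators". It mentions no Oahu restriction and no race mix specific to age or sex.

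**Race, Section 3.3.** Census-based estimates are to be made "with the assumption that the membership of the health plans is representative of the geographic base from which cases are drawn". For prevalence that base is Oahu.

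**Race, Hawaii site section 4.1.1.** For the planning figures, "we applied proportions based on the 2000 Census data for Hawaii". For the study period itself, "membership data from the health plans will either be geocoded to estimate race/ethnicity proportions and/or a survey of a random sample of members" is to supply the race information.

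**The concern.** Section 4.2 opens by requiring that the cases counted come from the same population that forms the denominator. The four geographic centers meet this by using the Census for the area that cases are drawn from, by age, gender and race. Southern California applies race percentages by single year of age and gender (its site section 4.1). Only Hawaii's rule in 4.2 takes race from a wider area than the cases and holds the mix constant over age.

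Three descriptions of the method also stand side by side with nothing to say which prevails, and they can give different race-specific denominators. Section 8.1.1 promises rates by race and by age down to single years, and national estimates adjusted for age, sex and race. Hawaii matters most for two groups with few cases elsewhere, Asians and Pacific Islanders (PI).

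**Working it through.** **1. Reproduce the Oahu table.** Inputs are the Oahu counts (Hawaii 4.1.2) and the statewide counts (Hawaii 4.1.3).
- Oahu ÷ state, PI aged 0–9: 20,914 / 26,143 = 0.800.
- Oahu ÷ state, Asian aged 10–19: 54,984 / 68,730 = 0.800.
- All 12 age-by-race cells lie between 0.799 and 0.800.
- PI share on Oahu: 20,914 / 115,325 = 18.1% at 0–9 and 22,657 / 124,935 = 18.1% at 10–19.
- Asian share on Oahu: 50,754 / 115,325 = 44.0% and 54,984 / 124,935 = 44.0%.

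The Oahu figures are thus the state figures times 0.80, with one race mix for both age bands.

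**2. Hawaii's weight in the pooled prevalence rates** (denominators from Table 6-1, cases from Table 4-2).
- PI: 43,571 / 80,309 = 54.3% of the denominator; (45 + 112) / 238 = 66.0% of expected cases.
- Asian: 105,738 / 254,480 = 41.6% of the denominator; (25 + 185) / 336 = 62.5% of expected cases.
- Non-Hispanic white, African American and Hispanic: 2.4%, 2.1% and 7.2% of the denominator.

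**3. Reproduce the stated precision.** With p = cases / N, the relative half-width is 1.96 × √(p(1−p)/N) / p.
- PI: p = 238 / 80,309 = 2.96 per 1,000, half-width 12.7%.
- Asian: p = 336 / 254,480 = 1.32 per 1,000, half-width 10.7%.

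Both match Table 6-1. The formula covers sampling error only and treats N as known.

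**4. Effect of a wrong share.** Let the true Oahu share be (1 + d) times the applied share. The reported Hawaii rate is then (1 + d) times the true one. With w the weight from step 2, the crude pooled rate is (1 + w·d) times the true one. The values of d are assumptions, because the documents give no race distribution for Oahu.

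| Assumed d | PI, pooled | Asian, pooled |
|---|---|---|
| ±5% | ±2.7% (2.96 against 2.89–3.05) | ±2.1% (1.32 against 1.29–1.35) |
| ±10% | ±5.4% (2.96 against 2.81–3.13) | ±4.2% (1.32 against 1.27–1.38) |

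At d = 10% the other three pooled rates move by 0.24%, 0.21% and 0.72%.

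**5. How large can d be?** Oahu is about 80% of the state (Hawaii 4.1.2). If S is the state share and O and N are the Oahu and neighbor-island shares, then S = 0.8·O + 0.2·N. Putting O = S(1 + d) gives N = S(1 − 4d). So d = 5% needs neighbor islands 20% away from the state share, d = 10% needs 40%, and d = 20% needs 80%.

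**6. Can such differences occur?** Two other centers' tables bear on this.
- Geography, South Carolina Appendices 1 and 2: the African American share is 80,098 / 184,757 = 43.4% in the four prevalence counties and 409,856 / 1,135,778 = 36.1% statewide, a ratio of 1.20.
- Age, Seattle Table 1: the Asian/PI share is 19,884 / 233,732 = 8.5% at 0–4 and 24,550 / 234,093 = 10.5% at 15–19, a ratio of 1.23.

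Neither figure measures Hawaii. They show only that equal shares across areas or ages cannot be taken for granted.

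**7. Where the flat age mix acts.** One share s applied to age counts M_a sums to s × ΣM_a. If members' ages resemble the Census population's, the 0–19 race total is unaffected by variation over age. The error then falls on race-by-age cells and on estimates built from them.

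**The case against.** The strongest reply is that the plan already contains the remedy. The Hawaii site section reserves Census proportions for planning and assigns geocoding or a member survey to the real study. Its tables are projections that rest on a disclosed assumption of the same age split in every race group. On that view the 0.80 scaling shows how the projections were built, not how the 2001 rates will be calculated. Section 3.3 and the alignment principle in 4.2 also allow the statewide wording to be read as loose drafting.

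Much of this stands. The tables confirm what the 4.2 rule produces but do not prove that reported rates will use it. The reply does not remove the conflict: 4.2 is written as the rule for the study, and nothing subordinates it to the site section.

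A reader might infer that every race-specific Hawaii rate is wrong. The documents do not support that, because an error needs Oahu's mix to differ from the state's, or the mix to vary by age, and no county shares are given. A reader might also take the rule to use all-age proportions; its text says ages 0–19. Nor is the overall Hawaii prevalence affected, since cases and members are both limited to Oahu.

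**Conclusion.** The point holds as an unresolved inconsistency with a possible bias, not as a demonstrated one. Section 4.2 as written uses a population wider than the case base and a flat age mix, and it disagrees with Section 3.3 and Hawaii 4.1.1.

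The size rests on an assumed 5–10% relative error in the applied share: about 3–5% on the crude pooled PI rate and about 2–4% on the Asian rate, direction unknown. This is bias outside the stated intervals of ±12.7% and ±10.7%. These are crude pooled rates as in Table 6-1; weights in the nationally adjusted estimates would differ. A 20% error, which would move the pooled PI rate by about 11% (0.543 × 20%), is tempting to quote. It would need neighbor-island shares 80% away from the state's, and nothing in the documents supports that. Other groups' pooled rates are barely touched. The Oahu mismatch does not arise for incidence, which is statewide.

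**What to change.** Make Sections 3.3 and 4.2 and Hawaii 4.1.1 name the same primary method for the 2001 prevalence race denominators, restricted to Oahu and specific to age and sex. Either of two choices would do:
- Census 2000 proportions for Honolulu County by age group and sex, applied to Oahu membership; or
- the geocoding or survey already foreseen in Hawaii 4.1.1, confined to Oahu members.

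The first needs only different lookup tables but still assumes that members resemble residents. A survey measures members directly, and zip codes are already in the membership files. The choice can stay with the investigators, provided it is stated. Use the other method as a sensitivity check on the pooled Asian and PI rates, and keep statewide proportions, by age and sex, for incidence only. The cost is different Census tables and a small amount of extra analysis; the Census option needs no new data collection.

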4.2.1. Prevalence Component**4.2.1.1. Eligibility Criteria**

The eligibility criteria for prevalent cases of diabetes are as follows:

- a. Prevalent in 2001,

- b. Age less than 20 years on December 31, 2001; this corresponds to a birth year: 1/1/82 – 12/31/2001 for the prevalence year of 2001. Subjects reaching age 20 in the prevalence year are not eligible,
- c. Resident of the population defined for prevalent cases at any time in the prevalence year (for geographically-based centers) or member of the participating health plan in the prevalence year,
- d. Not active-duty military,
- e. Not living in an institution (defined as such by the Census),
- f. Not gestational diabetes.

For geographically-based centers, resident is defined to align numerator and denominator and includes anyone documented to have resided in that center's geographical area at any time during the prevalence year.

Prevalent cases of diabetes in active duty military personnel are ineligible because it is anticipated that access to military medical records will be difficult. It is unlikely that the prevalent diabetes cases will be present among active duty military because diabetes precludes active duty military service.

Prevalent cases of diabetes in dependents of military personnel having access to civilian medical facilities will be eligible, recognizing that prevalent diabetes cases receiving care only at military facilities can be ascertained only if access to military records is obtained.

Prevalent cases of diabetes in college students are eligible for SEARCH as these youth are counted in the Census as resident at their college address. Additionally, college students identified as cases by membership-based centers cannot be removed from the membership-based administrative records that are the source of denominator data for these centers.

4.2.1.2. Case Finding Approaches

The approach to case-finding for prevalent cases varies by center as a reflection of availability of an existing diabetes registry or database and access to clinics, physicians, and computer-stored data resources. The data sources that will be used to ascertain cases include: hospital administrative data, hospital discharge records, laboratory records, prescription records, ambulatory administrative records, ambulatory clinical records (including: pediatric and adult endocrine practices, and primary care practices); diabetes registries; state insurance plans; and vital records.

For geographically based centers, database searches for potential cases may be retrospective to January 1, 1998, if data are available. Case searches in databases prior to this date were shown to be less effective (unpublished data, Colorado and South Carolina) in terms of locating eligible cases. The center-specific protocols for case ascertainment provide detail on the case finding approaches for each SEARCH center.

Table 4-1 summarizes the data sources that will be used at each center to identify prevalent cases.

Table 4-1. Data Sources Used to Identify Prevalent Cases by Center

Center	Hospital Discharge	Laboratory	Prescription	Ambulatory Billing	Pediatric Endocrinology Case List	Other
Cincinnati	x			x	x	x
Colorado	x			x	x	x
Hawaii	x	x	x	x	x	x
Seattle	x			x	x	x
S. Carolina	x			x	x	x
S. California		x	x			

4.2.1.3. Case Validation

It is important that cases of diabetes be true cases of diabetes. For prevalent cases, the information that is necessary to establish that the case meets the ADA criteria for diabetes will not be accessible, due to lack of chart review.

Prevalent cases of diabetes are validated if the case has either:

- a. a physician diagnosis of diabetes; or
- b. parent or youth self-reports a physician diagnosis of diabetes at the time of an interview or survey.

A “physician diagnosis” of diabetes is made if any of the following conditions are met:

- a. review of any medical record reveals a physician diagnosis of diabetes;
- b. the diagnosis of diabetes is directly verified, or the diabetes case is “referred” to the study, by a clinician;

- c. diabetes is listed as the underlying or contributing cause of death on a death certificate;
- d. the case is included in a clinical database that has a requirement for verification of diagnosis by a clinician.

4.2.1.4. Estimated Number of Prevalent Cases

The estimated number of prevalent cases that will be identified by center, age, race/ethnicity and type is shown in Table 4-2. These estimates were based on prevalence of type 1 and type 2 diabetes derived from the literature and unpublished data available to SEARCH investigators (see Table 4-2), which were applied to the center-specific denominator estimates by age group and race/ethnicity.

Table 4-2. Estimated Number of Prevalent Cases by Center, Age Group, and Race/Ethnicity.

Age	NHW	AA	Hispanic	Asian	PI	N.Am	Total
0 thru 9							
California	178	33	63	4	7	0	285
Colorado	317	23	35	0	1	25	401
Hawaii	27	3	7	25	45	0	107
Ohio	246	32	0	0	0	0	278
Seattle	402	33	16	6	8	3	468
S Carolina	46	38	1	0	0	0	85
10 thru 19							
California	463	115	342	47	27	2	996
Colorado	677	64	159	10	5	114	1,029
Hawaii	73	11	47	185	112	0	428
Ohio	646	112	0	0	0	0	758
Seattle	985	98	79	59	33	13	1,267
S Carolina	127	142	7	0	0	0	276
Total	4,187	704	756	336	238	157	6,378

4.2.2. Incidence Component of SEARCH

4.2.2.1. Eligibility Criteria

The beginning year for identification of incident cases is 2002. Identification of incident cases will continue for the duration of the study.

The eligibility criteria for incident cases of diabetes are as follows:

Onset of diabetes (January 1 through December 31) in the incidence year; “onset of diabetes” is the date of first clinical diagnosis of diabetes in a non-pregnant state

- a. Age less than 20 years on December 31 of the onset year. Participants who turn 20 in the onset year are not eligible.
- b. Resident of population defined for incident cases in the onset year (for geographically-based centers) or member of the participating health plan in the onset year.
- c. Not active duty military.
- d. Not living in an institution (defined as such by the Census).
- e. Not gestational diabetes.

For geographically-based centers, resident is defined to align numerator and denominator and includes anyone documented to have resided in the geographic area for that center at any time during the onset year.

